### **3. Appendix 1 – TLF shells**

**Table 14.2.1.42**  
Time to Achieve Intervention of Rescue Therapy  
(Full Analysis Set)

|   | K-321 QID
(N=XXX) | K-321 BID
(N=XXX) | Placebo
(N=XXX) |
|---|----------------------|----------------------|--------------------|
| Patients with Intervention of Rescue Therapy, n (%)           | XX (XX.X)            | XX (XX.X)            | XX (XX.X)          |
| Time to Archive Intervention of Rescue Therapy [day] (95% CI) |                      |                      |                    |
| 25th  | XX.X (XX.X, XX.X)    | XX.X (XX.X, XX.X)    | XX.X (XX.X, XX.X)  |
| 50th (Median)   | XX.X (XX.X, XX.X)    | XX.X (XX.X, XX.X)    | XX.X (XX.X, XX.X)  |
| 75th  | XX.X (XX.X, XX.X)    | XX.X (XX.X, XX.X)    | XX.X (XX.X, XX.X)  |

p-value [1]

Note: NA = Not Applicable

Patient is considered having received rescue therapy if the patient 1) received rescue surgical procedure (penetrating keratoplasty or endothelial keratoplasty) during the study. 2) withdrawal with potential for surgical procedure. 3) withdrawal with potential for Rho kinase Inhibitor treatment.]

Patient's study discontinuation date is used as the rescue therapy date if the patient withdrawal with potential for surgical procedure or Rho kinase Inhibitor treatment.

Patients who completed follow-up or discontinued the study without receiving rescue therapy were [REDACTED]

[1] Two-sided p-value is from the log rank test.

Table 14.2.1.43

Central Corneal ECD (cells/mm^2) of Study Eye performed by Specular Microscopy by Visit (LOCF) via Wilcoxon Rank Sum Test (Full Analysis Set)

|                                   | K-321 QID
(N=XXX) | K-321 BID
(N=XXX) | Placebo
(N=XXX) |
|-----------------------------------|----------------------|----------------------|--------------------|
| Central Corneal ECD at Baseline   |                      |                      |                    |
| n                                 | XX                   | XX                   | XX                 |
| Mean (SD)                         | XX.X (XX.XX)         | XX.X (XX.XX)         | XX.X (XX.XX)       |
| Median                            | XX.X                 | XX.X                 | XX.X               |
| Q1, Q3                            | XX.X, XX.X           | XX.X, XX.X           | XX.X, XX.X         |
| Min, Max                          | XX, XX               | XX, XX               | XX, XX             |
| Difference to Placebo [1]         |                      |                      |                    |
| p-value by Wilcoxon Rank Sum Test | X.XXXX               | X.XXXX               |                    |
| Hodges-Lehmann Estimate           | X.X                  | X.X                  |                    |
| Moses 95% Confidence Interval     | (XX.X, XX.X)         | (XX.X, XX.X)         |                    |
| Central Corneal ECD at Week 1     |                      |                      |                    |
| n                                 | XX                   | XX                   | XX                 |
| Mean (SD)                         | XX.X (XX.XX)         | XX.X (XX.XX)         | XX.X (XX.XX)       |
| Median                            | XX.X                 | XX.X                 | XX.X               |
| Q1, Q3                            | XX.X, XX.X           | XX.X, XX.X           | XX.X, XX.X         |
| Min, Max                          | XX, XX               | XX, XX               | XX, XX             |
| Difference to Placebo [1]         |                      |                      |                    |
| p-value by Wilcoxon Rank Sum Test | X.XXXX               | X.XXXX               |                    |
| Hodges-Lehmann Estimate           | X.X                  | X.X                  |                    |
| Moses 95% Confidence Interval     | (XX.X, XX.X)         | (XX.X, XX.X)         |                    |

...  
 Note: LOCF = last-observation-carried, ECD = Endothelial Cell Density  
 Baseline is defined as the last measurement including unscheduled assessments prior to the administration of first dose of [REDACTED] treatment.  
 Central corneal ECD (both baseline and post-baseline) that are unable to be performed due to corneal oedema are [REDACTED]. Assessment images that are unable to be analysed and categorized as [REDACTED].

[REDACTED] and [REDACTED] by [REDACTED] are [REDACTED]  
[REDACTED]  
[REDACTED]  
[REDACTED]  
[REDACTED] is based on the Wilcoxon rank sum test. The [REDACTED] between [REDACTED] treatment groups and the Moses CIs were estimated with the Hodge-Lehmann method.  
Source Data: Listing 16.2.6.1

<DIRECTORY PATH>PROGRAM NAME Executed: DDMMYYYY hh:mm

Prog Notes: 1. Repeat for scheduled visits.

Table 14.2.1.44

Change from Baseline in Central Corneal Thickness ( $\mu\text{m}$ ) of Study Eye by Visit (LOCF) via Wilcoxon Rank Sum Test  
(Full Analysis Set)

|   | K-321 QID
(N=XXX) | K-321 BID
(N=XXX) | Placebo
(N=XXX) |
|---|----------------------|----------------------|--------------------|
| Change from Baseline in
Central Corneal Thickness at
Week 1 [1] |                      |                      |                    |
| n   | XX                   | XX                   | XX                 |
| Mean (SD)   | XX.X (XX.XX)         | XX.X (XX.XX)         | XX.X (XX.XX)       |
| Median  | XX.X                 | XX.X                 | XX.X               |
| Q1, Q3  | XX.X, XX.X           | XX.X, XX.X           | XX.X, XX.X         |
| Min, Max  | XX, XX               | XX, XX               | XX, XX             |
| Difference to Placebo [2]   |                      |                      |                    |
| p-value by Wilcoxon Rank
Sum Test                                  | X.XXXX               | X.XXXX               |                    |
| Hodges-Lehmann Estimate   | X.X                  | X.X                  |                    |
| Moses 95% Confidence
Interval                                      | (XX.X, XX.X)         | (XX.X, XX.X)         |                    |

Note: Baseline is defined as the last measurement including unscheduled assessments prior to administration of first dose of study eye drops. The values for the change from baseline in central corneal thickness and the values for the change from baseline in corneal topography are [REDACTED].

Change from baseline is defined as the post baseline value minus the baseline value for the given assessment. For the change from baseline, only patients with a value at both baseline visit and the specific post-baseline visit are included.

[2] P-value is based on the Wilcoxon rank sum test. The median differences between the treatment groups and the Moses CIs were estimated with the Hodge-Lehmann method.

Source Data: Listing 16.2.6.3

<DIRECTORY PATH>PROGRAM NAME Executed: DDMMYYYY hh:mm

Prog Notes: Repeat for scheduled visits.

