4.2.1 Reasons for Discontinuation or Withdrawal

Patients may discontinue treatment or withdraw from the study at any time and for any reason without prejudice to their future medical care by the investigator or at the study site. Every effort must be made to keep patients in the study. The reasons for patients discontinuing treatment or withdrawing early will be recorded.

A patient may discontinue treatment or be discontinued from treatment for any of the following reasons:

1. The patient does not meet the protocol inclusion or exclusion criteria.
2. The patient is non-compliant with the protocol.
3. The patient has a serious or intolerable AE that, in the investigator's opinion, requires withdrawal from the study.
4. The patient has symptoms or an intercurrent illness not consistent with the protocol requirements or that justify withdrawal.
5. The patient undergoes rescue keratoplasty (Section 5.8.2).
6. Other reasons (eg, pregnancy, development of contraindications of use of study drug).

A patient may be withdrawn from the study for any of the following reasons:

1. The patient withdraws consent.
2. The patient is lost to follow-up.

The investigator will also withdraw all patients if Kowa Research Institute, Inc. terminates the study. The study may be terminated if it becomes apparent that the objectives of the trial cannot be met, or if the frequency or pattern of AEs reported in the trial indicate that the drug is no longer likely to have a positive benefit-to-risk ratio.

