4.2.2 Handling of Withdrawals

Patients who withdraw from the study or who are withdrawn from the study will no longer receive study drug. When a patient withdraws or is withdrawn from the study, the reason(s) for withdrawal shall be recorded by the investigator on the relevant page of the electronic case report form (eCRF).

Whenever possible, all patients who withdraw from the study early will undergo all EOS assessments. Patients who fail to return for final assessments will be contacted by the site with 2 documented telephone calls followed by 1 registered letter, as needed, to have them comply with the protocol.

It is vital to obtain follow-up data on any patient withdrawn because of an AE or serious AE (SAE). In every case, efforts must be made to undertake protocol-specified safety follow-up procedures.

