7.7 Statistical Analysis Methodology

Statistical analysis will be performed using SAS software Version 9.4 or later. Continuous variables will be summarised using the mean, the SD, median, minimum value, and maximum value. Categorical variables will be summarised using frequency counts and percentages. Unless otherwise noted, the denominator to determine the percentage of participants in each category will be based on the number of participants with available data. Selected ordinal data may be summarised using both descriptive statistics and counts and percentages of participants in each category, as appropriate. Data will be listed in data listings.

Details of the statistical analyses, methods, and data conventions are described in the statistical analysis plan (SAP).

All statistical tests will be 2-sided and performed using a 0.05 significance level, leading to 95% (2-sided) CIs.

A closed 2-step ordered testing procedure will be used to control overall type I error for the primary efficacy endpoint, central corneal ECD at Week 12. In step 1, the K-321 0.4% QID group will be statistically compared with the placebo group. If the step 1 comparison is significant, step 2 will be performed to statistically compare K-321 0.4% BID group with the placebo group. If the statistical comparison made during step 1 is not significant, testing will still be performed to compare the BID group to placebo; however, all p values will be considered nominal/descriptive only.

No other measures will be taken to control error for the multiple secondary and exploratory endpoints or multiple treatment comparisons.

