## 1. Introduction

This statistical analysis plan (SAP) addendum to the primary SAP v2.0, dated August 25, 2021, is to describe additional analyses that were defined **after the Week 12 Unmasking** to support the final CSR. All analyses that were defined in the primary SAP v2.0 prior to the Week 12 unmasking will not be described again in this document.

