## 2. Additional Analyses

The additional analyses will be performed for the Full-analysis set.

The following time-to-event endpoint will be analysed by pairwise log-rank tests comparing each active K-321 0.4% treatment regimen to placebo. Kaplan-Meier estimates and plots will also be presented up to Week 52. Patients who complete follow-up or discontinue the study without achieving the specified endpoint will be censored [REDACTED]

- Time to Intervention of Rescue Therapy\*

\*Patient is considered having received rescue therapy if the patient [REDACTED]

The following endpoints based on continuous measures will be analysed by pairwise Wilcoxon rank sum tests comparing each active K-321 0.4% treatment. For [REDACTED] Central corneal Endothelial Cell Density (ECD) assessments, the [REDACTED] data handling methods will be the same as primary analysis, or the Central corneal ECD assessments that could not be performed due to oedema. Otherwise, the [REDACTED] data will be [REDACTED]

[REDACTED]. Patients who receive a rescue keratoplasty will be [REDACTED] or [REDACTED] by [REDACTED], [REDACTED] or [REDACTED], respectively.)

For assessments other parameters, the [REDACTED] data will be [REDACTED]. Additionally, the mean values and standard deviation (SD) by visit will be graphically displayed.

- Central corneal ECD of study eye performed by specular microscopy at [REDACTED]
- Central corneal thickness change from [REDACTED] to [REDACTED].
- BCVA (letters) by ETDRS change from [REDACTED] to [REDACTED]

The following endpoint based on the number and percentage of patients achieving the endpoint will be analysed by Pearson chi-square test comparing each active K-321 0.4% treatment regimen to placebo. The 95% CI for the difference in percentage of patients achieving the endpoint will also be presented. Should the number of responders be less than 5 in either group, Fisher's exact test will be used instead. If Fisher's exact test is used, the unconditional confidence interval for the difference in response rates will be provided. The missing data will be [REDACTED]. Patients who receive a rescue keratoplasty will be [REDACTED]. Additionally, the number and percentages of subjects achieving endpoint by visit will be graphically displayed

- Number and percentage of patients who achieve no corneal oedema

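### The post-unmasking time-to-rescue endpoint counts withdrawals with only potential for later treatment as rescue received, with no readable criterion, and near the threshold one such call can move the log-rank p-value across 0.05

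*SAP*

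**What the plan says.** The addendum's Introduction describes its contents as "additional analyses that were defined after the Week 12 Unmasking to support the final CSR". Its section 2 adds time to intervention of rescue therapy in the full-analysis set, followed to Week 52, which "will be analysed by pairwise log-rank tests comparing each active K-321 0.4% treatment regimen to placebo". The event definition in that section is redacted.

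The notes to Table 14.2.1.42 and Figure 14.2.1.42 state the definition legibly. The first event is a penetrating or endothelial keratoplasty carried out during the study. The other two are "2) withdrawal with potential for surgical procedure. 3) withdrawal with potential for Rho kinase Inhibitor treatment". For these two, "Patient's study discontinuation date is used as the rescue therapy date".

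On withdrawal, Protocol 4.2.1 states that "A patient may be withdrawn from the study for any of the following reasons", then lists withdrawn consent and loss to follow-up; sponsor termination is mentioned separately. Protocol 4.2.2 adds that "the reason(s) for withdrawal shall be recorded by the investigator on the relevant page" of the eCRF. Protocol 5.8.2 describes rescue as keratoplasty only, and such patients remain in follow-up. Protocol 5.6.1 keeps the investigator and site staff masked until the end of the study, except where medical care requires unmasking.

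**The concern.** A keratoplasty is an observed fact with its own date. The other two events depend on someone deciding that a patient who left had potential for surgery or for a Rho kinase inhibitor. Two patients who leave on the same day can therefore enter the analysis differently, one as an event and one as censored, on that decision alone.

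The definition was written once Week 12 treatment codes had been opened. If the person deciding knew the arm, that knowledge could influence which withdrawals are called rescue. With about 20 patients per arm and probably few events, a single decision may carry weight in a pairwise test read at the protocol's two-sided 0.05 level (Protocol 7.7). The addendum contains no analysis restricted to keratoplasties performed against which a reader could judge this.

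**Working it through.** **Inputs from the documents.** 20 patients per group, about 60 in total (Protocol 7.4 and 4.1; 3 × 20 = 60 agrees). Pairwise log-rank against placebo (addendum section 2). Two-sided 0.05 (Protocol 7.7). About 5% withdrawal by Week 12 (Protocol 7.4), so 0.05 × 20 = 1 patient per arm.

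**No figure to reproduce.** The documents give no event count or power for this endpoint, and the effect size, SDs and powers behind n = 20 are redacted.

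**Assumptions.** Event counts are assumed. Within each arm events are equally spaced inside Weeks 13 to 38, and everyone else is censored at Week 52.

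**Formula.** At each event time let n be the number at risk, n0 those on placebo and d the events. E = Σ d·n0/n and V = Σ d·(n0/n)(1 − n0/n)(n − d)/(n − 1). With O the observed placebo events, χ² = (O − E)²/V on 1 df.

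**Worked case, 0 active against 4 placebo events.**
- E = 20/40 + 19/39 + 18/38 + 17/37 = 1.920 and V = 0.997. χ² = (4 − 1.920)²/0.997 = 4.34, p = 0.037.
- Treat the earliest placebo event as a censored withdrawal on the same day: E = 19/39 + 18/38 + 17/37 = 1.420, V = 0.747, χ² = (3 − 1.420)²/0.747 = 3.34, p = 0.068.
- Treat the latest one that way: E = 20/40 + 19/39 + 18/38 = 1.461, V = 0.749, χ² = (3 − 1.461)²/0.749 = 3.16, p = 0.075.

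**Same check for other counts.** The range covers which placebo event is censored.

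| Active vs placebo events | p, all counted | p, one placebo event censored instead |
|---|---|---|
| 0 vs 4 | 0.037 | 0.068 to 0.075 |
| 1 vs 6 | 0.040 | 0.070 to 0.079 |
| 2 vs 8 | 0.029 | 0.0497 to 0.057 |
| 3 vs 9 | 0.041 | 0.067 to 0.075 |

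Other spacings of the events move some p-values slightly; 1 vs 6 becomes 0.044, for example.

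**Opposite direction.** One active-arm withdrawal coded as an event rather than censored moves 0 vs 4 from 0.037–0.042 to 0.14–0.17.

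**Away from the threshold.** Going from 0 vs 2 to 0 vs 3 moves p from 0.152 to 0.075; from 0 vs 5 to 0 vs 6, from 0.018 to 0.009. Neither crosses. Take active counts 0 to 4 and placebo counts from the active count up to 10, omitting 0 vs 0. There are 10 + 10 + 9 + 8 + 7 = 44 pairs, and one extra placebo event crosses 0.05 in 5 of them.

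**How often it could matter.** In 2,000 simulated trials per setting, each withdrawal was tried in turn as an event. Where the assumed rescue rates differed (active 0–10%, placebo 10–34%), at least one such recoding crossed 0.05 in 19–38% of trials with 5% withdrawal and 24–56% with 15%. With equal rates it was 3–8%. These are upper figures, because every withdrawal is treated as open to reclassification.

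**The case against.** A reader might infer that the classification was made with knowledge of treatment. The documents do not show this. The Introduction does not say who was unmasked, Protocol 5.6.1 keeps sites masked, and under Protocol 4.2.2 it is the investigator who records the reason.

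A reader might also infer that no data field supports the two withdrawal events. That is not shown either. The two entries in Protocol 4.2.1 are grounds for withdrawal, and nothing makes them the only reasons the eCRF can hold. Because Protocol 5.8.3.2 prohibits ROCK inhibitors throughout, leaving to use one is a concrete reason that may have been recorded. Criteria could also stand in the redacted part of addendum section 2 or in SAP v2.0. These objections stand and limit the point to what can be read.

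The tabulated pairs were chosen near 0.05, and one extra keratoplasty would move p as far as one extra withdrawal event. That is correct: the fragility comes from 20 per arm. What distinguishes the withdrawal events is that their coding depends on a judgement.

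Finally, a keratoplasty-only analysis censors patients who left to seek treatment. They are likely failures, so that censoring may be informative, and counting them as events is a recognised response. This stands as a reason to show both analyses without ranking one as main.

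**Conclusion.** The point holds in a limited form. An endpoint defined after the Week 12 unmasking counts two kinds of withdrawal as rescue therapy received on their potential alone, with no readable criterion and no readable masking of the decision. Near the threshold one call can change which side of 0.05 the pairwise test falls on; 2 vs 8 is borderline, and elsewhere the call does not matter. The claim that one patient will decide the test is not supported, because the documents give no event counts.

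The size rests on 20 analysed per arm and on assumed counts and times. The analysis is openly labelled as post-unmasking, is not a protocol primary or secondary endpoint, and has no multiplicity control. The primary ECD conclusion does not depend on it. The change is still worth making, since it is cheap and reduces a possible bias.

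**What to change.** 1. Report a log-rank and Kaplan-Meier analysis of keratoplasty performed alongside the composite, without naming either as main.
2. Count the two withdrawal events only where the investigator's recorded withdrawal reason states planned surgery or planned Rho kinase inhibitor use.
3. Freeze the list of those patients from a listing without treatment codes before the table is run.
4. Show the number of each event type by arm.
5. Label the p-values descriptive.

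The cost is addendum wording, one frozen list and one extra run. The extra run has fewer events, so its p-value may be less favourable, and its censoring may be informative; the composite beside it lets the reader see how much that matters. If criteria and a masked review already exist in the redacted text or in SAP v2.0, items 2 and 3 reduce to a cross-reference.
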